8.11.2.7 Monitoring and Oversight

RBR samples will be tracked in a manner consistent with Good Clinical Practice by a quality-controlled, auditable, and appropriately validated laboratory information management system, to ensure compliance with data confidentiality as well as adherence to authorized use of samples as specified in this protocol and in the Informed Consent Form. Sponsor monitors and auditors will have direct access to appropriate parts of records relating to an individual's participation in the RBR for the purposes of verifying the data provided to the Sponsor. The site will permit monitoring, audits, IRB/EC review, and health authority inspections by providing direct access to source data and documents related to the RBR samples.

9. STATISTICAL CONSIDERATIONS

9.1 STATISTICAL HYPOTHESES

No formal statistical hypotheses will be tested for this study. All analyses will be conducted using descriptive statistics.

9.2 SAMPLE SIZE DETERMINATION

Approximately 30 participants will be randomly assigned to study treatment (15 in balovaptan arm and 15 in placebo arm) to perform the final analysis with reduced scope.

9.3 ANALYSIS SETS

The following populations are defined:

Participant Analysis Set	Description
Intent to treat	All participants randomly assigned to study drug. Participants will be analyzed according to the treatment to which they were assigned.
Safety evaluable	All participants randomly assigned to study drug and who receive at least one dose of study drug. Participants will be analyzed according to the treatment they actually receive.
PK evaluable	The PK-evaluable population will include all participants who receive at least one dose of balovaptan and have sufficient evaluable concentrations to determine the overall exposure to balovaptan. Participants may be excluded from the PK-evaluable population if they significantly violate the inclusion or exclusion criteria, deviate significantly from the protocol, or if data are unavailable or incomplete. Excluded cases will be documented together with the reason for exclusion. All decisions about exclusions from the analysis will be made prior to database lock.

PK=pharmacokinetic.

9.4 STATISTICAL ANALYSES

The intent-to-treat (ITT) analysis set, as defined in 9.3, will be used for efficacy analyses. The safety analysis set, as defined in 9.3, will be used for safety analyses.

Final database lock to enable the analysis of the primary and secondary endpoints will occur once all patients have either completed their follow-up assessment or withdrawn from the study early, and all data required for analysis have been cleaned and verified.

9.4.1 General Considerations

For all endpoints, baseline will be defined as the last assessment made up to and including the day of first study drug intake.

In general, descriptive statistics will be used to summarize continuous endpoints and counts and percentages will be used to summarize categorical endpoints.

Missing values will not be replaced.

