^a Concentration of M2 and M3 may be measured if indicated (e.g., safety concern).

The clinical question of interest is to assess the study treatment effect of 10 mg QD balovaptan compared with placebo in terms of the change from baseline at Week 12 in the Clinician-Administered PTSD Scale for DSM-5 (CAPS-5) irrespective of adherence to randomized treatment.

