7. DISCONTINUATION OF STUDY TREATMENT AND PARTICIPANT DISCONTINUATION OR WITHDRAWAL

An excessive rate of withdrawals (either because of participant discontinuing study drug or withdrawal from the study) can render the study non-interpretable. Therefore, unnecessary withdrawal of participants should be avoided and all efforts should be taken to motivate participants to comply with all the study specific procedures and to be followed until the end of the 12-week treatment period.

Before permanently discontinuing study drug (either initiated by the participant or the investigator), an interruption should be considered (see [Appendix 6](#), Section [A6–2.2](#) for further details). Participants, who temporarily discontinue study drug for any reason, should restart as soon as medically justified in the opinion of the investigator.

The investigator should show due diligence and explore all possible options to reach a participant who fails to return to a visit. The site must document all attempts to try to contact the participant in the source documents.

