7.1 DISCONTINUATION OF STUDY TREATMENT

It may be necessary for a participant to permanently discontinue (definitive discontinuation) study treatment. If study treatment is definitively discontinued, the

participant will remain in the study for additional assessments. Refer to the schedule of activities (see Section 1.3) for data to be collected at the time of discontinuation of study treatment and for any further follow-up evaluations that need to be completed.

Participants must permanently discontinue study treatment if they experience any of the following:

- Any medical condition that the investigator or Sponsor determines may jeopardize the participant's safety if he or she continues to receive study treatment
- Investigator or Sponsor determination that treatment discontinuation is in the best interest of the participant
- Pregnancy
- Inability of participant to continue to comply with study requirements
- Suicidal ideation score of 4 or 5 or category 6 or greater on the C-SSRS
- Specific events that are described in Sections 7.1.1, 7.1.2, 7.1.3, and 7.1.4

The primary reason for study treatment discontinuation should be documented on the appropriate eCRF.

All participants who withdraw or discontinue from the study treatment early will be asked to return as soon as possible (and within 2 weeks after the last dose of study drug) for an early discontinuation visit and complete the assessments as per the schedule of activities in Section 1.3 (see Table 1). Participants will also be asked to return for assessments of the primary and secondary efficacy outcomes at the end of the 12-week planned visit, regardless of their adherence to treatment. If the time between the early discontinuation visit and the 12-week planned visit is fewer than 2 weeks, then participants are exempted from the 12-week planned visit. If the time between the early discontinuation visit and the previous visit is fewer than 2 weeks, then participants are exempted from completing again all the primary and secondary assessments at the early discontinuation visit.

Refer to the schedule of activities in Section 1.3 (see Table 1) for details on follow-up assessments to be performed for participants who permanently discontinue study treatment. If a participant requests to be withdrawn from treatment or follow-up assessments, this request must be documented in the source documents and signed by the investigator.

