8.1.1.1 Clinician-Administered PTSD Scale for DSM-5 (CAPS-5)

The CAPS-5 is a 30-item structured interview that can be used to make current (past month) diagnosis of PTSD, make lifetime diagnosis of PTSD, or assess PTSD symptoms over the past week (Weathers et al. 2013a, 2018; see [Appendix 11](#)). For this study the past week version of the CAPS-5 will be used and will be administered by central rater. Items are scored using a 5-point scale, rated from 0 (absent) to

4 (extreme/incapacitating), with a higher overall score indicating a worse outcome. In addition to assessing the 20 DSM-5 PTSD symptoms, questions asked target the onset and duration of symptoms, subjective distress, impact of symptoms on social and occupational functioning, improvement in symptoms since a previous CAPS administration, overall response validity, overall PTSD severity, and specifications for the dissociative subtype (depersonalization and derealization). Responses will be collected by means of free text to understand intensity and frequency of symptoms, which are then used to select a response on a 5-point Likert scale, ranging from 0 (absent) to 4 (extreme/incapacitating). A total score is calculated by summing severity scores for items 1–20, where a higher score corresponds to greater severity of PTSD or presence of PTSD. Symptom cluster severity scores can also be derived by summing the individual item severity scores for symptoms corresponding to a given DSM-5 cluster: Criterion B (items 1–5); Criterion C (items 6–7); Criterion D (items 8–14); and, Criterion E (items 15–20). For each symptom, standardized questions and probes are provided. Administration requires identification of an index traumatic event to serve as the basis for symptom inquiry via the Life Events Checklist for DSM-5 (LEC-5; see Section 8.1.1.4 for more detail). The LEC-5 will be administered prior to the CAPS-5 at screening only. The CAPS was designed to be administered by clinicians and clinical researchers who have a working knowledge of PTSD but can also be administered by appropriately trained paraprofessionals.

The full interview takes 45–60 minutes to administer. In this study, the past week version of the CAPS-5 will be administered remotely by a central assessor. This first CAPS-5 assessment will be administered no more than 7 days prior to the baseline and at Week 6 and Week 12.

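### The primary Week 12 CAPS-5 summary is observed-case: it leaves out ITT participants with no Week 12 score, and no planned estimate uses their Week 6 score to inform Week 12

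*Combined protocol and SAP*

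**What the plan says.** The clinical question in Section 3 (after Table 2) is the effect on CAPS-5 change at Week 12 "irrespective of adherence to randomized treatment". Section 9.4 states: "The intent-to-treat (ITT) analysis set, as defined in 9.3, will be used for efficacy analyses". Section 9.3 defines that set: "All participants randomly assigned to study drug. Participants will be analyzed according to the treatment to which they were assigned".

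Data collection follows the question. Under Section 7.1, people who stop study drug stay in the study: "Participants will also be asked to return for assessments of the primary and secondary efficacy outcomes at the end of the 12-week planned visit". That request carries no condition on whether the drug was taken. Section 9.4.2 repeats the commitment.

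The analysis rule is brief. Section 9.1 rules out formal hypotheses and makes all analyses descriptive, and Section 9.4.1 adds "Missing values will not be replaced". The combined document gives no other missing-data rule for the primary endpoint. On timing, Section 8.1.1.1 says: "This first CAPS-5 assessment will be administered no more than 7 days prior to the baseline and at Week 6 and Week 12". The schedule of activities also places a CAPS-5 at the early discontinuation visit.

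**The concern.** The ITT set contains everyone randomized, but a Week 12 mean without imputation or a model contains only those with a Week 12 score. A score can be absent in three ways:

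- the participant withdraws from the study (Section 7.2);
- the participant is lost to follow-up (Section 7.3);
- the Week 12 visit is waived because the early discontinuation visit fell fewer than 2 weeks before it (Section 7.1).

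In the third case a CAPS-5 may exist close to Week 12, but no text says whether it counts. People who leave are not replaced (Section 4.1), so with 15 per arm each missing person is about 7% of the arm (1/15).

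With no hypothesis test, the by-arm CAPS-5 summary is the primary result. If people leave because they are not improving, the mean of those who remain overstates improvement. If that happens more in one arm, the comparison moves too. Section 7 recognizes the risk: "An excessive rate of withdrawals (either because of participant discontinuing study drug or withdrawal from the study) can render the study non-interpretable". The stated response is retention effort; nothing in the analysis addresses it. Section 9.4.6.1 summarizes study discontinuation, not missing CAPS-5 scores.

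**Working it through.** **Plan's own figure.** Section 9.2 gives about 30 participants. At 1:1 this is 30/2 = 15 per arm, which agrees. No SD, effect, correlation or missing rate is stated, so everything below is illustrative.

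**Step 1: arithmetic of an observed-case mean.** Bias of an arm mean = m × (mean of observed − mean of missing), where m is the share missing at Week 12. Bias of the difference is the difference of the two arm biases. Assumed gaps in CAPS-5 change are 0, 5 and 10 points.

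| Missing | Gap 0 | Gap 5 | Gap 10 |
|---|---|---|---|
| Arm mean, 1 of 15 | 0 | 0.33 | 0.67 |
| Arm mean, 3 of 15 | 0 | 1.00 | 2.00 |
| Arm mean, 5 of 15 | 0 | 1.67 | 3.33 |
| Difference, 3 vs 3 | 0 | 0 | 0 |
| Difference, 2 vs 4 | 0 | 0.67 | 1.33 |
| Difference, 1 vs 5 | 0 | 1.33 | 2.67 |

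Example: (5 − 1)/15 × 10 = 2.67. Bias is zero when nothing is missing or when missingness is unrelated to outcome.

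**Step 2: simulation with dropout tied to response.** Assumptions: 15 per arm, SD of change 11, Week 6 to Week 12 correlation 0.6, true Week 12 changes −9 (placebo) and −14 (balovaptan), so a true difference of −5. Week 6 means are about −6 and −9, or −6.5 and −10. Dropout is logistic, 4000–6000 replicates per scenario. In the placebo-only rows, the balovaptan arm has none or a random 25% missing. The repeated-measures estimate for two visits is obtained by regressing Week 12 on arm and Week 6 among those observed, then averaging over all Week 6 scores in each arm.

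| What drives dropout | Observed-case difference | Repeated-measures difference |
|---|---|---|
| Week 6 score, same in both arms, 20–35% missing | about −5.0 (each arm mean 1.6 to 2.3 too favourable) | −5.0 |
| Week 6 score, placebo only, 20–35% missing | −2.6 to −3.2 | −5.0 |
| Lack of effect in both arms, 15% vs 30% missing | −3.8 | not computed |
| Dropout before Week 6, placebo only, 30% | −2.5 | −2.5 |
| Unseen Week 12 score, placebo only | −0.9 to −1.5 | −2.3 to −2.6 |

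In the second row the distortion is 5.0 − 3.2 = 1.8 to 5.0 − 2.6 = 2.4 points.

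**Step 3: effect of the return visit.** Take 30% placebo-only dropout with an observed-case difference of −2.5, a bias of 2.5. The leavers' mean then lies 2.5 × 0.70/0.30 = 5.8 points from the full-arm mean. If 80% of them return, 6% remain missing and the bias is 5.8 × 0.06/0.94 = 0.4, giving about −4.6. Simulation gave −4.8.

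**Step 4: scale.** With about 25% missing, 15 × 0.75 = 11.25 per arm remain, and the sampling SD of the difference is 11 × √(2/11.25) = 4.6. The repeated-measures estimate had no larger sampling SD (4.6 against 4.7, or 4.4–4.8 against 4.4–4.9).

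**Visit rules side by side.** Section 7.1 waives Week 12 when the early discontinuation visit is fewer than 2 weeks before it. Footnote c of the schedule of activities instead waives the early discontinuation visit when withdrawal is within 2 weeks of Week 12. The two passages must be reconciled before anyone can say which CAPS-5 will exist.

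**The case against.** The strongest objection is that the plan is descriptive on purpose. The amendment cut the study from 252 to 30 participants and removed the estimand description and analysis methodology because the smaller sample precludes formal comparisons. On this view a model with an adjusted difference and interval brings back what was removed. One part stands: Section 9.1 as written does not allow the model and would need amending. The rest does not. An estimate with a 95% CI and no test is not a formal comparison, and the model replaces no missing value.

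Second, the simulation suits the remedy, because dropout driven by the Week 6 score is the case the model handles. This stands. The model gains nothing for dropout before Week 6 and only part of the loss when dropout follows the unseen Week 12 score.

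Third, the bias is about half the sampling SD and no error rate is affected. This also stands, and it limits the weight of the point.

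A reader might also infer that the Week 6 CAPS-5 is discarded or that by-arm means are the only efficacy output. Neither is so. Week 6 change is an exploratory endpoint (Table 2) summarized under Section 9.4.4, and Section 9.4.3 adds CGI-S counts and a PHQ-9 shift table. The Week 6 score simply does not inform the Week 12 estimate.

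**Conclusion.** The point holds as a limitation that can be reduced cheaply. The primary summary describes participants with a Week 12 CAPS-5, on or off treatment, within a nominal ITT set. Under the assumptions above, the bias is about 2 points in an arm mean and up to about 2 points in the difference when response-related dropout is confined to one arm. It is a few tenths of a point if most who stop treatment return. Dropout driven by unseen Week 12 status could distort the difference more.

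Three stronger readings are not supported:

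- That this is a treatment-completer analysis: off-treatment Week 12 scores are sought and included.
- That it cannot answer the question as stated: non-adherence and missing data are different things, and the question goes unanswered only to the extent that Week 12 scores are absent.
- That the arm means are biased: the documents give no missing rate, so neither size nor direction can be shown.

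**What to change.** Keep the observed-case table and make four additions.

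1. In Section 9.4.2, add a repeated-measures summary of CAPS-5 change at Weeks 6 and 12. Terms: baseline score, arm, visit, arm-by-visit; unstructured covariance. Include all ITT participants with at least one post-baseline CAPS-5, with off-treatment scores. Report adjusted arm means and their difference with a 95% CI and no hypothesis test.
2. Amend Section 9.1 so that estimation without testing is permitted.
3. Tabulate availability of the Week 12 CAPS-5 by arm and reason. This also shows how many people left before Week 6, whom the model cannot recover.
4. State how a CAPS-5 from an early discontinuation visit is used when the Week 12 visit is waived, and reconcile Section 7.1 with footnote c of the schedule.

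The cost is a few lines of text, the change to Section 9.1 and a small amount of programming. No extra data are needed. The downside is a missing-at-random assumption, which should be stated together with its limits: it does not cover dropout before Week 6 or dropout driven by unobserved Week 12 status.

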9.4.2 Primary Endpoint

The primary endpoint is the change in CAPS-5 total symptom severity score from baseline at Week 12, as defined in Section 3 (see Table 2). The change from baseline in CAPS-5 total symptom severity score at Week 12 will be calculated as the score at Week 12 minus the score at baseline. A negative change from baseline in CAPS-5 total symptom severity score indicates improvement.

Every effort will be made to minimize missing data. Participants who discontinue early from study treatment will be asked to return for collection of safety and limited efficacy data (i.e., the primary and secondary efficacy endpoints) at the scheduled visits.

9.4.3 Secondary Endpoints

The secondary endpoints are the changes from baseline at Week 12 in the CGI-S and PHQ-9, as defined in Section 3 (see Table 2).

9.4.3.1 Clinician-Global Impression of Severity (CGI-S)

The change from baseline in CGI-S will be calculated as the CGI-S score at Week 12 minus the CGI-S score at baseline. A negative change from baseline in CGI-S indicates improvement.

The count and percentages for each value of CGI-S changes will be evaluated.

9.4.3.2 Patient Health Questionnaire-9 (PHQ-9)

The PHQ-9 is a 9-question instrument to assess presence and severity of depression (see Section 8.1.1.3 for details). The total sum of responses score ranges from 0 to 27 and will be summarized using descriptive statistics at each assessment timepoint for absolute values as well as change from baseline. Additionally, the score will be categorized as shown in Table 5, and a shift table will be provided to examine changes in depression severity categories from baseline to worst post-baseline depression severity.

Table 5 Patient Health Questionnaire-9 (PHQ-9) Score and Corresponding Categories

PHQ-9 Score	Depression Severity
0–4	None-minimal
5–9	Mild
10–14	Moderate
15–19	Moderately severe
20–27	Severe

PHQ-9=Patient Health Questionnaire-9

9.4.4 Exploratory Endpoints

Exploratory endpoints as defined in Section 3, [Table 2](#), will be analyzed descriptively by treatment arm. Descriptive statistics (mean, standard deviation, median, and range) will be presented for continuous variables and counts and percentages will be presented for categorical variables.

The relationship between biomarkers (see Section [8.7](#)) and efficacy, safety, PK, or other biomarker endpoints *may* be explored to identify biomarkers that are predictive of response to balovaptan or are early signs of efficacy.

9.4.5 Safety Analyses

Safety will be assessed through summaries of exposure to study treatment, adverse events, physical and neurologic examinations, urine drug screens, changes in laboratory test results, changes in vital signs, ECGs and Doppler echocardiograms (where applicable), and C-SSRS.

Study treatment exposure (such as treatment duration and treatment compliance) will be summarized with descriptive statistics.

All verbatim adverse event terms will be mapped to Medical Dictionary for Regulatory Activities thesaurus terms, and adverse event severity will be graded according to mild, moderate, or severe scale (see Adverse Events Severity Grading Scale; [Appendix 3, Table 1](#)). All adverse events, serious adverse events, adverse events leading to death, adverse events of special interest, and adverse events leading to study treatment discontinuation that occur on or after the first dose of study treatment (i.e., treatment emergent adverse events) will be summarized by mapped term, appropriate thesaurus level, and severity grade. For events of varying severity, the highest grade will be used in the summaries. Deaths and cause of death will be summarized.

Relevant laboratory, vital sign (pulse rate, respiratory rate, blood pressure, and temperature), and ECG data will be displayed by time, with grades identified where appropriate. Additionally, a shift table of selected laboratory tests will be used to summarize the baseline and maximum post-baseline severity grade. Changes in vital signs and ECGs will be summarized.

9.4.6 Other Analyses

9.4.6.1 Summaries of Conduct of Study

Enrollment, study treatment administration, and discontinuation from the study will be summarized by treatment arm. The reasons for study treatment discontinuation will also be tabulated. Major protocol deviations, including major deviations with regard to the inclusion and exclusion criteria, will be summarized by treatment arm.

9.4.6.2 Summaries of Treatment Group Comparability

Demographics and baseline characteristics (including age, sex, type of trauma [veteran/*armed forces service-related* or civilian], concurrent antidepressant use, time since triggering event, and time since PTSD diagnosis) will be summarized by treatment arm. Baseline data are the last data obtained prior to initiation of study treatment. Descriptive statistics (mean, standard deviation, median, and range) will be presented for continuous variables and counts and percentages will be presented for categorical variables.

9.4.6.3 Pharmacokinetic Analyses

Individual and mean plasma concentrations of balovaptan at each sampling timepoint will be presented by listings and descriptive summary statistics, including means, medians, geometric means, ranges, standard deviations, and coefficients of variation. If warranted by the observed data, empirical Bayes estimates for individual balovaptan PK parameters and exposure may be derived using a previously developed population PK model (1101622 [available upon request]). Concentration of M2 and M3 may be measured if indicated (e.g., safety concern) and presented in listings and descriptive summary statistics.

Graphical exploration of the relationship between balovaptan exposure and outcome measures and biomarkers as well as safety parameters may be performed. If indicated by such exploration, more formal analyses of PK to pharmacodynamic (PD), safety or efficacy measures of interest may be undertaken.

Results of population PK or PK/PD model-based analyses may be reported in a separate study summary.

